### 4.3 JUSTIFICATION FOR DOSE

The air flow rates to be used in this study were determined based on the results of a tolerability study conducted with the CoolStat device using double nostril flow. In this study, 80% of the subjects (4 of 5) in the highest flow arm (48 LPM) tolerated the dose provided (24 LPM per nostril), which is expected to provide the best reduction in migraine symptoms, i.e., the higher the dose (air flow rate), the better local cooling and reduction of symptoms. In the double nostril flow configuration, the total dose is halved per nostril. Thus, 24 LPM was chosen as our high flow dose for this single nostril tolerability study. Based on this, we expect that many subjects will be able to tolerate the higher flow, but not all. As such, we are proposing to test both a high flow as well as a lower flow, to better assess:

- Tolerability at the highest dose setting in the single nostril air flow configuration
- The dose-response on outcomes, i.e., the relation between dose and symptom reduction

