### 6.1.3 DOSING AND ADMINISTRATION

There will be two active treatment doses and one sham dose evaluated in this study: a high flow (24 LPM) dry air, a low flow (18 LPM) dry air, and the sham flow (6 LPM) of ambient air. All treatment arms will be administered through blinded, pre-set settings on the CoolStat device. Study personnel will be provided an input number, e.g., 1-9 (to put in the CoolStat user screen) that correlates to the two active treatment arms as well as the sham arm. Redundant numbers are used to help protect the blinding process. When the CoolStat is turned on, it displays a series of user-friendly set up instructions on its display screen. The final step in the startup process involves inputting the ‘input number’, which will be done for each subject.

A randomization process will be used with the proposed study to assign the numerical input value and desiccant cartridge selection (A, B or C) for each subject at each site. We have arranged to use MedNet to support this work, including their cloud-based randomization tool. For example, when a particular study site receives a new subject, study personnel will log on to the MedNet database, which will then provide both a device numerical input value and a cartridge designation based on a preset randomly generated list for this study. For example, the study inputs may be 4C, or 5A or 9B, which would correspond to a high therapy arm, a low therapy arm and a sham arm, respectively. This will ensure that the treatment is assigned randomly to each subject and there will be no risk of the device being pre-programmed to the incorrect flow rate (i.e. from a prior subject).

More detail on the device startup process can be found in the Operator’s Manual and CoolStat QuickStart Guide.

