## 9 STATISTICAL CONSIDERATIONS

### 9.1 STATISTICAL HYPOTHESES

- Primary Efficacy Endpoint(s):
  1. Dose response comparison for pain relief at 2 hours

- a. Null hypothesis:  
 $H_0: \pi_A - \pi_S = 0$ ; where  $\pi_A$  is the proportion of subjects who show pain relief at 2 hours after active treatment (flow rate of x or Y) and  $\pi_S$  is the equivalent value for the sham-control treatment group.
  - b. Alternative hypothesis:  
 $H_a: \pi_A - \pi_S > 0$ ; where  $\pi_A$  is the proportion of subjects who show pain relief at 2 hours after active treatment (flow rate of x or Y) and  $\pi_S$  is the equivalent value for the sham-control treatment group.
- Secondary Efficacy Endpoint(s):
    1. Dose response comparison for pain relief immediately and 24 hours post treatment.
      - a. Null hypotheses:
        - i.  $H_0: \pi_A - \pi_S = 0$ ; where  $\pi_A$  is the proportion of subjects who show pain relief immediately after active treatment (flow rate of x or Y) and  $\pi_S$  is the equivalent value for the sham-control treatment group.
        - ii.  $H_0: \pi_A - \pi_S = 0$ ; where  $\pi_A$  is the proportion of subjects who show pain relief at 24 hours after active treatment (flow rate of x or Y) and  $\pi_S$  is the equivalent value for the sham-control treatment group.
      - b. Alternative hypothesis:
        - iii.  $H_a: \pi_A - \pi_S > 0$ ; where  $\pi_A$  is the proportion of subjects who show pain relief immediately after active treatment (flow rate of x or Y) and  $\pi_S$  is the equivalent value for the sham-control treatment group.
        - iv.  $H_a: \pi_A - \pi_S > 0$ ; where  $\pi_A$  is the proportion of subjects who show pain relief at 24 hours after active treatment (flow rate of x or Y) and  $\pi_S$  is the equivalent value for the sham-control treatment group.
    2. Dose response comparison for pain freedom immediately, 2 hours, and 24 hours post treatment.
      - a. Null hypotheses:
        - i.  $H_0: \pi_A - \pi_S = 0$ ; where  $\pi_A$  is the proportion of subjects who show pain freedom immediately after active treatment (flow rate of x or Y) and  $\pi_S$  is the equivalent value for the sham-control treatment group
        - ii.  $H_0: \pi_A - \pi_S = 0$ ; where  $\pi_A$  is the proportion of subjects who show pain freedom 2 hours after active treatment (flow rate of x or Y) and  $\pi_S$  is the equivalent value for the sham-control treatment group.

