## 9.2 SAMPLE SIZE DETERMINATION

We conducted a preliminary study using an alpha prototype of our cooling device in which subjects were blinded to the treatment. In that study, 56% of subjects in the dry air treatment group reported freedom from headache pain at two hours post treatment compared to 8% of subjects in the sham group. A power analysis using this effect size as a basis for calculation indicated a minimum sample size of 17 patients in each group would be required to achieve at least 80% power to detect a significant difference at two-tailed alpha level = 0.05. We realize that the effect size from this initial study seems quite large, and we propose a conservative  $n=25$  per group to account for error in estimates based on the preliminary results, for a total sample size of 75 subjects.

100 subjects will be consented to account for screen failures. Only the first 75 subjects who return with a qualifying migraine will be randomized to a treatment group.

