#### 9.4.2 ANALYSIS OF THE PRIMARY EFFICACY ENDPOINT(S)

Both primary efficacy endpoints are scored categorically (Grade 0: no pain, Grade 1: mild pain, Grade 2: moderate pain, Grade 3 severe pain).

These categorical data will be summarized by absolute (n) and relative (%) frequency tables.

For categorical variables/proportions, we will perform Kruskal-Wallis test (the nonparametric equivalent of the ANOVA) to determine if there is a difference across the three study groups.

If there is a difference, then the Mann-Whitney test will be performed to compare the groups to each other to determine where the difference lies. We will correct for multiple comparisons using Bonferroni correction. The multiple imputation method will be used as the primary method for handling missing data in this study.

---

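### The plan sets out to assess dose-response, but no planned test uses the order of the arms; a pre-specified, supportive ordered analysis with the 24 v 18 LPM estimate would fill the gap cheaply

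*Combined protocol and SAP*

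**What the plan says.** Section 4.3 names two things that testing two flows should help to assess. The second is "The dose-response on outcomes, i.e., the relation between dose and symptom reduction". The same section gives the expected direction: "the higher the dose (air flow rate), the better local cooling and reduction of symptoms". Finding the optimal dose is part of the primary objective (sections 1.1 and 3).

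Section 9.1 heads the primary efficacy hypothesis "Dose response comparison for pain relief at 2 hours" and uses the same label for secondary items 1 to 4. Each hypothesis is nevertheless written as one active arm minus sham. There is no trend parameter and no contrast between the two active flows.

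Section 9.4.2 will "perform Kruskal-Wallis test (the nonparametric equivalent of the ANOVA) to determine if there is a difference across the three study groups". It continues: "If there is a difference, then the Mann-Whitney test will be performed to compare the groups to each other", and "We will correct for multiple comparisons using Bonferroni correction". The number of comparisons is not given. Section 9.4.3 carries the same methods to the secondary endpoints. No trend test, ordered contrast or slope appears anywhere.

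Section 6.1.3 defines the arms as "a high flow (24 LPM) dry air, a low flow (18 LPM) dry air, and the sham flow (6 LPM) of ambient air". Sham therefore differs from the active arms in humidity as well as in flow.

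**The concern.** Kruskal-Wallis gives the same p-value however the three arms are labelled. It can show that the groups differ but says nothing about whether response rises with flow. The pairwise step does include 24 v 18 LPM, but only after a significant overall test and at a reduced alpha, with 25 subjects on each side.

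The trial could therefore finish with no prespecified summary of the relation that section 4.3 sets out to assess. If an ordered analysis were added after unblinding, the choice of test and scores would be open to the data. That choice matters: in the calculations below, the scores alone move power by up to 10 points in the plateau and reversed cases.

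**Working it through.** **The plan's own figure.** Section 9.2 starts from these prototype results: "56% of subjects in the dry air treatment group reported freedom from headache pain at two hours post treatment compared to 8% of subjects", the 8% being the sham arm. From them it derives 17 per group for at least 80% power at two-sided 0.05. Exact Fisher power for 56% v 8% is 77.4% at n = 16 and 81.3% at n = 17, so 17 reproduces. This is a two-group calculation on pain freedom. The documents give no power for the three-group test, no rate for 18 LPM and no sham rate for pain relief.

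**Inputs.** From the documents: 25 per arm (9.2), 1:1:1 allocation (6.3), two-sided 0.05 (9.2), flows 6, 18 and 24 LPM. Assumed: all response rates other than 8% and 56%, and three pairs for Bonferroni. Section 9.1 speaks of proportions and 9.4.2 of grades 0 to 3, so both forms were examined.

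**Formulas for a yes/no outcome.** Let x be the count of responders per arm, n = 25, N = 75, p the pooled proportion and q = 1 - p.

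- Kruskal-Wallis: H = (N-1)/N × Σ(x - np)² / (npq), critical value 5.991 (2 df).
- Cochran-Armitage with scores s: z = Σ(s - s̄)x / √(npq Σ(s - s̄)²). Reject if z² > 3.841 (1 df).

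**One case by hand, rates .20/.40/.50 (sham/18/24).** Expected counts are 5, 10 and 12.5, so p = 27.5/75 = .367, np = 9.17 and npq = 5.81. The squared deviations sum to 17.36 + 0.69 + 11.11 = 29.17, so H = (74/75) × 29.17/5.81 = 4.96, below 5.991. With scores 6, 18, 24 (mean 16; deviations -10, 2, 8), the numerator is -50 + 20 + 100 = 70 and the denominator is √(5.81 × 168) = 31.2. So z = 2.24 and z² = 5.02, above 3.841. The signal is nearly the same, but the ordered test spends one degree of freedom on it instead of two.

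**Power by exact enumeration of three binomials.**

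| Sham/18/24 | Kruskal-Wallis | Trend, scores 6/18/24 | Trend, scores 0/1/2 | Gain (points) |
|---|---|---|---|---|
| .20/.40/.50 | 51.5% | 63.4% | 62.8% | +12, +11 |
| .25/.39/.53 | 42.7% | 52.7% | 56.5% | +10, +14 |
| .30/.45/.60 | 47.5% | 56.9% | 62.2% | +9, +15 |
| .08/.24/.40 | 67.4% | 79.0% | 78.8% | +12, +11 |
| .08/.32/.56 (protocol's ends, assumed midpoint) | 94.9% | 97.8% | 97.6% | +3, +3 |
| .20/.50/.50 (plateau) | 62.8% | 68.3% | 62.7% | +5, 0 |
| .08/.40/.40 (plateau) | 80.0% | 83.5% | 73.4% | +3.5, -7 |
| .20/.20/.50 (threshold) | 65.5% | 53.8% | 64.6% | -12, -1 |
| .20/.50/.40 (18 LPM better) | 51.5% | 42.5% | 32.0% | -9, -20 |
| .30/.30/.30 (null) | 4.8% | 5.1% | 4.9% | none |

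**Four-grade scale.** Simulation under proportional odds gives a gain of 9 to 11 points for near-linear effects with a linear rank trend test. A separate Jonckheere-Terpstra simulation (assumed sham grades 0 to 3 of 8/22/40/30%) is similar: 52% to 64% at relief 30/44/59%, 38% to 49% at 30/41/54%, and 73% to 81% at 30/54/66%. It loses at a plateau (30/59/59%: 65% to 62%) and when 18 LPM is better (30/59/49%: 53% to 32%).

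**What the planned sequence can show about flow alone.** This is the probability that Kruskal-Wallis rejects and 24 LPM then beats 18 LPM at 0.05/3 two-sided (z > 2.394):

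- .20/.40/.50: 4%
- .25/.39/.53: 8%
- .30/.45/.60: 9%
- .08/.24/.40: 12%
- .08/.32/.56: 24%

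**What a trend test would not show.** At .30/.59/.59 the two flows are equal, yet Cochran-Armitage rejects in 63% (scores 6/18/24) or 59% (scores 0/1/2) of trials, because both active arms beat sham. If the trend test were a second unadjusted 0.05 test, the chance under the null that either it or Kruskal-Wallis rejects would be about 7% to 8% at common rates of 20% to 40%.

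**The case against.** The case for leaving the plan alone is substantial.

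- The formal hypotheses in 9.1 are active-minus-sham differences, and the pairwise tests address them. That stands. What is missing is an analysis of the section 4.3 aim, not of the hypotheses as written.
- A reader might infer that the trial could say nothing for or against dose-response. The documents do not support that: 9.4.2 plans 24 v 18 LPM among its pairwise comparisons and tabulates the grades by group. The comparison is weak, but it exists.
- An order-blind overall test is defensible. The objective is the optimal dose, which need not be the highest. Section 4.3 expects that some subjects will not tolerate the higher flow, and the ITT set in 9.3 keeps those who stop early. Response could peak at 18 LPM, where an ordered test loses. This stands, and it is why the ordered test should not replace Kruskal-Wallis.
- A three-arm trend is not purely a flow trend, because sham also uses ambient air (6.1.2, 6.1.3). A significant trend may mean only that active beats sham. This stands and limits what the trend may be used to claim.
- A second 0.05 test on the primary outcome would need an error-rate rule. This stands, and is met by placing the test outside the primary error-rate claim.

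**Conclusion.** The gap is real and can be read from the text: there is a stated dose-response aim with an expected direction, but no planned analysis that uses the order. The only flow-only contrast is gated and would show 24 LPM better in about 4% to 24% of trials under the assumed rising rates.

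A reader might go further and say that the plan gives up a fixed amount of power, around ten points. The documents do not support that. The gain of 9 to 15 points (9 to 11 on the grades) rests on assumed moderate, near-linear responses. At the only effect size in the documents, Kruskal-Wallis already has about 95% power and the gain is 2 to 3 points. That effect is for pain freedom, not the primary pain relief, and section 9.2 itself calls it large, so moderate scenarios are reasonable, but they remain assumptions. The gain runs from about +5 to -7 for a plateau and is negative if 18 LPM does better.

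This is a low-cost improvement. It does not make the primary analysis invalid.

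**What to change.** Leave the 9.4.2 tests unchanged as the primary analysis, and add to 9.1 and 9.4.2:

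1. One pre-specified ordered analysis of the 2-hour outcome: Jonckheere-Terpstra with sham < 18 < 24 LPM, or Cochran-Armitage with scores fixed in advance if relief is analysed yes/no. Label it supportive, outside the primary error-rate claim, and not to be used to claim an effect of an individual dose.
2. The 24 v 18 LPM difference or odds ratio with a 95% CI, reported whatever the Kruskal-Wallis result, as the only contrast that isolates flow.
3. A statement that the three-arm trend also carries the difference between dry and ambient air.

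The cost is a few sentences, with no new data or subjects. There are three downsides. Power is low if response peaks at 18 LPM. A significant trend may reflect active v sham alone. The 24 v 18 LPM interval will be wide: at assumed rates of 45% and 60% its half-width is 1.96 × √(.45×.55/25 + .60×.40/25) = 27 points. That width is still useful to report, because it shows how little 25 per arm can settle about flow.

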#### 9.4.3 ANALYSIS OF THE SECONDARY ENDPOINT(S)

Our secondary outcomes (pain relief and relief from symptoms at 2 hours, 24 hours and immediately after treatment) are graded on the same scale, and the same statistical methods used as for the primary outcomes will be used.

All relevant general, safety and efficacy data will be descriptively summarized at each time point.

Continuous data will be summarized by the number of patients (n), the arithmetic mean and the standard deviation, the coefficient of variation as a percentage (CV%), the median, the interquartile range, the minimum and the maximum value.

---

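### Within one endpoint, Bonferroni after the three-group Kruskal-Wallis gate adds no needed multiplicity protection and costs power; the plan is valid but conservative

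*Combined protocol and SAP*

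**What the plan says.** Section 9.4.2 describes the outcome as graded pain: "Both primary efficacy endpoints are scored categorically", on Grades 0 to 3. A Kruskal-Wallis test is run "to determine if there is a difference across the three study groups". If it shows one, "the Mann-Whitney test will be performed to compare the groups to each other to determine where the difference lies". Then: "We will correct for multiple comparisons using Bonferroni correction". On missing data: "The multiple imputation method will be used as the primary method for handling missing data in this study".

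The section gives no alpha for the gate and no Bonferroni divisor. It does not say whether the correction covers only the pairs or also endpoints and time points. Section 9.4.3 carries the approach to the secondary outcomes: "the same statistical methods used as for the primary outcomes will be used".

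The primary efficacy hypothesis in section 9.1 is headed "Dose response comparison for pain relief at 2 hours" and is written on proportions, active vs sham. Section 4.3 gives as one reason for having two active flows: "The dose-response on outcomes, i.e., the relation between dose and symptom reduction".

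**The concern.** The plan protects the pairwise tests twice: once by the gate and again by Bonferroni. If the gate already controls family-wise error for the three pairs, the second layer lowers power without being needed for multiplicity. With 25 per arm there is little power to spare, and the comparisons that describe dose-response (low dose vs sham, low vs high dose) start from the weakest position.

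**Working it through.** **The plan's own figure.** Section 9.2 gives 17 per group for 56% vs 8% pain freedom, 80% power, two-tailed 0.05. A two-sided Fisher exact test has power 77.4% at n = 16 and 81.3% at n = 17, so 17 reproduces. It is sized for one comparison at 0.05, with no multiplicity adjustment. The plan enrols 25 per group.

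**Why the gate is enough within an endpoint.** Let L, H and S be low dose, high dose and sham, with pairwise nulls of equal outcome distributions. A pair is declared different if the gate p-value is at most 0.05 and the pair's p-value is at most 0.05.

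- All three equal: any false claim needs the gate to reject, so error is at most 0.05.
- Exactly one pair equal: only that pair can be falsely claimed, so error is at most 0.05.
- Exactly two pairs equal: impossible, since two equalities force the third.
- No pair equal: no false claim can be made.

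This is closed testing and holds for exactly three groups, provided each test holds its own 5%.

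**Inputs for the size.** From the documents: 25 per arm, 1:1:1 allocation, 8% and 56%. Assumed: gate at 0.05; divisor 2 (0.025) or 3 (0.0167); all grade distributions; all relief and low-dose rates; all missing rates. Distributions over Grades 0/1/2/3:

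- Pain-free case: sham .08/.22/.40/.30, high dose .56/.16/.16/.12, midpoint .32/.19/.28/.21.
- Relief case: sham .08/.17/.40/.35, high dose .20/.33/.27/.20, midpoint .14/.25/.335/.275. Relief (Grade 0 or 1) is then 25% vs 53%.

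**Power on the graded score** (400,000 simulated trials per case, tie-corrected asymptotic tests):

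| Case | Comparison | Pairs at 0.05 | Divisor 2 | Divisor 3 | Loss (points) |
|---|---|---|---|---|---|
| Pain-free, low dose midway | low vs sham | 38.6% | 28.3% | 23.2% | 10.3 or 15.4 |
| | low vs high | 40.3% | 29.7% | 24.4% | 10.6 or 15.9 |
| | high vs sham | 88.7% | 87.7% | 86.2% | 1.0 or 2.5 |
| Pain-free, doses alike | active vs sham | 93.4% | 89.7% | 86.8% | 3.7 or 6.6 |
| Relief, low dose midway | low vs sham | 13.0% | 9.1% | 7.0% | 3.9 or 6.0 |
| | low vs high | 13.7% | 9.3% | 7.2% | 4.4 or 6.5 |
| | high vs sham | 36.1% | 33.5% | 30.5% | 2.6 or 5.6 |
| Relief, doses alike | active vs sham | 40.2% | 34.9% | 30.8% | 5.3 or 9.4 |

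If the low dose equals sham in the pain-free case, high vs sham loses about 3 or 6 points. A second set of assumed distributions (sham 8/27/40/25%, high dose 56/20/14/10%, low dose midway) gave the same pattern at divisor 3: low vs sham 40.1% to 24.3%, low vs high 41.5% to 25.4%, high vs sham 90.2% to 87.9%.

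**Error without Bonferroni, graded score.** Global null 4.8-4.9%; one true pair 4.3-4.9% in these cases. In a search over distributions with every grade at 5% or more, the worst cases were 5.0% on re-run. If nearly all scores fall on two grades, the asymptotic tests reach 6.3%. With multiple imputation (5% or 10% missing, D2 pooling of the gate statistic, Rubin's rules for the Mann-Whitney z), error was 4.5-5.3% and the losses were similar.

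**Binary outcome** (all 26³ outcomes enumerated). Exact gate and Fisher pairs at 0.05, against the plan's asymptotic tests with Bonferroni:

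| Rates S/L/H | Comparison | Exact, pairs at 0.05 | Plan, divisor 3 | Plan, divisor 2 |
|---|---|---|---|---|
| 8/32/56 | low vs sham | 45.2% | 36.8% | 46.3% |
| | low vs high | 33.3% | 23.9% | 33.4% |
| | high vs sham | 93.6% | 93.5% | 94.2% |
| 8/56/56 | active vs sham | 94.9% | 93.8% | 95.0% |
| 25/53/53 | active vs sham | 39.1% | 35.3% | 40.8% |

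Asymptotic pairs left unadjusted on a binary outcome reach 6.5% error. Permutation tests at both steps bring the true-pair error to about 3.5%. On the graded score they keep most of the gain: low vs sham 37%, against 23% under the plan at divisor 3.

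**The case against.** Bonferroni after an omnibus test is conventional and safe, and it protects the pairs without leaning on the gate. That stands. A reader might infer that section 9.4.2 is wrong or inflates error. It does neither; its error is at or below the nominal level.

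A reader might also infer that the Bonferroni sentence can simply be deleted. The documents do not support that, for three reasons.

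- **Scale.** Section 9.1 states its hypotheses on proportions, and section 8.1.2 records nausea, photophobia and phonophobia as yes/no, although section 9.4.3 describes one common scale. Section 9.4.3 would carry an unadjusted asymptotic rule to those binary outcomes, where error exceeds 5%. There, the Bonferroni margin absorbs an approximation error.
- **Family.** The purpose of the correction is not stated. Section 9.4.2 speaks of two primary efficacy endpoints, while section 9.1 lists one primary efficacy hypothesis. If Bonferroni is meant to span endpoints or time points, it is not redundant, because the gate does nothing across endpoints.
- **Where the loss falls.** The 10-16 point losses need an intermediate low dose and a high-dose effect near the planning value. Section 4.3 expects benefit to rise with flow, but the grade distributions are assumed. Low vs high dose is also not a section 9.1 hypothesis, although section 9.4.2 compares all groups with each other.

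Finally, high vs sham at the planning effect keeps 86-88% power with Bonferroni in the midpoint case, above the plan's 80% target. That also stands, and it keeps the point small.

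**Conclusion.** The point holds as a minor matter of efficiency. Within one endpoint and three groups, the gate plus unadjusted pairs already controls family-wise error, so Bonferroni across the pairs only costs power.

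On the graded score with a low dose midway and the planning effect, the cost is about 10 points (divisor 2) or 15-16 (divisor 3) for the two low-dose comparisons, and 1-3 for high vs sham. With a flat response or an inactive low dose it is about 3-4 or 6-7 for comparisons with a true effect. It would be too strong to say that the loss always falls mainly on the low dose.

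On a binary outcome at the plan's rates, exact tests gain about 8-9 points for the low-dose pairs and 0-1 for high vs sham against divisor 3, and nothing or slightly less than nothing against divisor 2.

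The redundancy is a logical result. The sizes rest on a gate at 0.05, the two divisors tried, and assumed grade distributions; only the 8%, the 56% and the 25 per arm come from the documents.

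**What to change.** In section 9.4.2, replace the Bonferroni sentence with text such as: *If the three-group Kruskal-Wallis test is significant at 0.05, each pairwise Mann-Whitney test is made at two-sided 0.05 (closed testing for three groups, within the endpoint). Permutation versions of both tests are used for every endpoint, including the binary responder and binary symptom outcomes.*

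Add two statements:

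- **Imputation.** State how both tests are combined across imputations. The D2 and Rubin's-rules check above used the asymptotic statistics, so the rule for permutation tests must be spelled out.
- **Endpoints.** State that 2-hour pain relief carries the 0.05 and that all other endpoints are supportive.

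If asymptotic tests are kept for binary endpoints, keep Bonferroni for those.

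The cost is a few sentences, with no extra patients or data. There are two downsides. Bonferroni is the plan's only multiplicity adjustment, so the rule across endpoints has to be written before it goes. Pairwise validity then relies on the gate, so no pair may be claimed when the gate is not significant.
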